#### 15. Drug Accountability

- g. The study personnel will account for all study medication dispensed to and returned from the patient.
- h. Patients will be asked to bring all unused study medication and empty packages to the site at each office visit. Any discrepancy between dispensed and returned study medication will be explained.
- i. Any patient found to be noncompliant would be counseled on the importance of taking their study medication as prescribed.

#### **Randomization and Blinding**

This is a double blinded, randomized, placebo-controlled trial in patients with heart failure. Computer-generated randomization tables will be provided by [name] at the Emory School of Public Health. Block randomization based on diabetes (with or without) status. The randomization tables will be mailed to each institution where a member of the research team will oversee the randomization process and group assignment.

#### **Procedures for unblinding the study:**

The treatment code should not be broken except in medical emergencies when the appropriate management of the patient requires knowledge of the treatment. The Emory University of Atlanta physician ([name] or delegate) should be consulted whenever possible prior to the investigator breaking the blind.

**Recruitment and Retention:** Potential study subjects will be identified and pre-screened among patients admitted with ADHF. For each center, a research coordinator will screen all admission daily to identify patients with a diagnosis of ADHF. Once a potential participant is identified, the research coordinator will first contact the primary care team/provider to discuss protocol (if needed) and request permission to approach patient and relatives. Then the research coordinator will approach the potential participant/and or family members to explain the purpose, intervention, and potential benefits/risks of participating in this study. A study coordinator will conduct informed consent in eligible subjects prior to any study procedures. Screening and recruitment reports will be generated weekly that include actual

and expected recruitment statistics. Strategies to address potential problems with recruitment will include weekly communications with Drs. [name] and research team.

**Subject retention and study adherence are the two most important barriers in research trials in hospital and post-discharge trials.** Our team has applied problem-solving approach to promote continued adherence in previous intervention studies, with adherence to previous inpatient/discharge trials exceeding 85%. During screening, participants and family members will be informed about which clinically intervention, treatment and relevant test and when these tests will be performed during the study. Only subjects who fully understand these commitments and appear likely to follow the study protocol will be enrolled. We will have dedicated study coordinators who will conduct screening and obtain consent for participation.

### **Withdrawal Criteria**

1. The subject may withdraw at will at any time.
2. The subject may be withdrawn from the trial at the discretion of the investigator due to a safety concern or if judged non-compliant with trial procedures or included in contravention to the inclusion and/or exclusion criteria.
3. Adverse events (AE), i.e., any clinical, laboratory abnormality or concurrent illness which, in the opinion of the investigator, indicates that continued participation in the study is not in the best interest of the patient.
4. Doubling of serum creatinine above the baseline value confirmed by a repeated measurement within one week (study medication can be discontinued and continue study visits as described in the premature treatment discontinuation).
5. Pregnancy or intention to become pregnant.

### **Subject Replacement**

There will be no replacement of subjects in this trial.

### **Unscheduled Visits**

Additional unscheduled phone and/or clinic visits may also be performed at any time during the study at investigator's discretion (abnormal results, etc.).

### **Premature Treatment Discontinuation:**

#### **Patient agrees to undergo the Premature Treatment Discontinuation Visit and then continue in-person study visits**

The patient agrees to undergo the Premature Treatment Discontinuation Visit (PTDV) as visit 9 and then continue in-person study visits according to plan. This is the preferred option and patients who discontinue study medication will always be asked if they agree to this approach. If agreed, as above, the patient will undergo their PTDV at the next scheduled office visit after the study medication is stopped. The patient will continue attending subsequent study visits according to schedule,

#### **Patient refuses to continue in-person study visits but agrees to undergo modified follow-up**

If the patient refuses to continue in-person study visits, but agrees to undergo modified follow up, the in-person PTDV visit (as visit 9) should be performed as soon as possible after the study medication is stopped. All subsequent visits until the end of study date will be done as modified follow-ups (e.g., regular telephone contacts, a contact at study closure, or other means) in order to ascertain whether any endpoints or safety events had occurred. Such a patient has not withdrawn his/her consent or withdrawn from the study.

### **Patient refuses any form of follow-up**

If the patient refuses any form of follow-up, he/she officially withdraws from the study and withdraws consent. This decision must be documented. At the end of the study, vital status on all such patients will be collected from publicly available sources, in accordance with local regulations.

### **Lost to follow up patients**

To prevent patients being lost to follow-up, patient's contact details, including next of kin contacts will be collected initially and updated regularly by the research team. The research coordinators will educate the patient on the importance of contact with the research team throughout the study. Repeated attempts will be made to locate and obtain pertinent medical information for patients who are initially lost to follow-up. A patient will be classified as lost to follow up only if he/she has failed to return for the required study visits and his/her vital status remains unknown despite multiple attempts to contact him/her via telephone, fax, e-mail, certified letter or through patient locator agencies (if allowed by national regulation). The informed consent forms will include language to grant the option to employ outside companies to assist in obtaining updated contact information or ascertainment of vital status of lost patients using publicly available source.

**Study Sites:** This study will be performed at 4 academic institutions:

**Grady M. Hospital: Endocrinology section:** [name], CDE (Principal investigator), [name], MPH, [name], [name], [name], MPH  
**-Cardiology section:** [name], MPH, [name]

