SGLT2-is have been shown to markedly reduced HF hospital admissions in patients with and without diabetes. In the CVD-Real Study, which included 961 HF cases, SGLT2-i reduced the rates of HF hospitalizations hazard ratio, 0.61; 95% confidence interval, 0.51-0.73; P<0.001. The CVD-Real 2 multinational study of 235,064 patients with T2D, initiation of an SGLT-2i was also associated with a lower risk of all-cause death and hospitalization for heart failure, as compared to other glucose lowering drugs. The use of SGLT-2i vs. other glucose lowering drugs was associated with lower risk of death and heart failure. Recent RCT examining cardiovascular outcome using SGLT2-i reported a significant reduction in hospitalization for HF. In the DECLARE trial, dapagliflozin resulted in lower rate of hospitalization for heart failure compared to placebo (HR, 0.73; 95% CI, 0.61 to 0.88). The EMPA-REG OUTCOME study showed a 35% reduction in HF hospitalizations. In addition, in the CANVAS Program the benefits were greater in patients with a previous history of HF compared with those without HF at baseline (HR, 0.87; 95% CI, 0.72–1.06; P interaction = 0.021). In the Canvas Program, the rate of HF was reduced in patients with history of HF from 28.1% to 14.1% between patients treated with canagliflozin and placebo.

Based on data summarized above, we assume the composite event rate in the placebo group is between 40-60%, which would be reduced by 30% in the dapagliflozin group. Based on two-sided Chi-square test, with preserved alpha=0.05, with 176 subjects, we would achieve over 80% power to detect a 30% reduction in proportion of patients with readmission, ER visits, urgent unplanned clinic visit for HF or death if the composite event rate in the placebo group is 50%. Accounting for 10% attrition, we propose to recruit 392 patients (196 per group).

In the table below, we provide estimated power based on the same method, corresponding to different placebo composite event rates that are between 40-60%:

Composite event rate in the placebo group	40%	45%	50%	55%	60%
Estimated Power	62%	72%	82%	88%	93%

The results in the above table suggest promising power for the proposed study.

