#### **Analysis of Primary Endpoint:**

We will first compare the proportion of patients with at least 1 readmission, ER visit or unplanned urgent clinic visit for HF or death between the two study groups, using Chi-squares test or Fisher’s Exact tests. Logistic regression will be conducted to adjust for the effects of other potential confounders (e.g. age, gender). Stepwise, backward, or forward model selection strategy will be adopted to determine the variables to be included in the final model. Standard diagnostic and model checking procedures,

such as deviance residual plot and Hosmer- Lemeshow test, will be applied to examine the fit of the developed models.

**Analysis of Secondary Endpoints:** The secondary endpoints include continuous longitudinal outcomes (e.g. change in KCCQ score from baseline at 6, 12, and 26 weeks), and discrete outcomes (e.g. whether patients with a  $\geq 5$ pts increase in KCCQ score). To analyze continuous longitudinal outcomes, we will first conduct cross-sectional analyses based on nonparametric Wilcoxon tests (or t-tests), followed by multivariate linear regression, where responses may be transformed to better meet the normality assumption. Then we will apply repeated measures ANOVA or repeated measures linear regression model to assess the outcome differences between the two study groups, simultaneously evaluating the outcomes measured at different time points while appropriately accommodating the within-subject correlations. For discrete outcomes, we will conduct univariate analyses based on Chi-square tests (or Fisher's Exact tests). For binary discrete outcomes, we will use logistic regression models to account for the effects of other potential confounders. For other types of discrete outcome (e.g. counts), we will apply Poisson regression models or Negative Binomial regression models to address the confounding effects of other variables. Standard model selection and checking procedures will be applied to ensure the adequacy of the adopted models.

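### Loss to follow-up ignores heart failure event status, and the primary chi-square has no valid place for patients known to be alive whose HF events are unknown

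*Combined protocol and SAP*

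**What the plan says.** - **Definition of loss** (Lost to follow up patients). A patient counts as lost only when the patient has "failed to return for the required study visits and his/her vital status remains unknown despite multiple attempts". Both conditions are needed, and neither concerns HF events. The sentence before it promises more: "Repeated attempts will be made to locate and obtain pertinent medical information for patients who are initially lost to follow-up".
- **Full refusal** (Patient refuses any form of follow-up). These patients are recorded as withdrawn, and "vital status on all such patients will be collected from publicly available sources". Nothing is said about HF events after withdrawal.
- **Modified follow-up** (for patients who decline in-person visits but accept contact). Contacts continue "in order to ascertain whether any endpoints or safety events had occurred".
- **Event capture.** Suspected endpoint events reach adjudication through the investigator and adverse event reports (Adjudication of suspected CV endpoints). Adverse events are collected up to the last visit or contact (Recording of adverse events).
- **Primary analysis** (Analysis of Primary Endpoint). The opening step reads: "We will first compare the proportion of patients with at least 1 readmission, ER visit or unplanned urgent clinic visit for HF or death". The test is a chi-square or Fisher's exact test, followed by logistic regression. The section gives no analysis set, no censoring and no rule for unknown status.
- **Sample size** (Sample Size and Power Calculations). 176 is raised to 196 per group for 10% attrition.

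**The concern.** Three of the four components of the composite are HF contacts, and public records can show a death but not an HF admission. Someone who leaves at week 4 and is later found alive is therefore not lost under the protocol, although 22 weeks of HF history are missing. A binary table has two ways to treat that person. Counting the person as event-free understates the arm's rate. Removing the person while keeping leavers who had an event before departure overstates it. If departure differs by arm, the treatment difference moves, and its direction depends on a coding choice that the plan leaves open. Some imbalance is conceivable, since Withdrawal Criteria allows withdrawal for safety or non-compliance. The vital-status definition would also make reported attrition look smaller than it is for the primary endpoint. The same unsettled coding could enter the per-group event rates used for sample size re-estimation.

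**Working it through.** **1. The plan's own figure.** Inputs from Sample Size and Power Calculations: 50% vs 35% (a 30% relative reduction), two-sided alpha 0.05, 176 (the figure reproduces only if this is per group), 10% attrition.

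Power = Φ{[|p1 − p2| − 1.96·√(2p̄(1 − p̄)/n)] / √([p1(1 − p1) + p2(1 − p2)]/n)}

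With n = 176 and p̄ = 0.425: (0.15 − 1.96 × 0.0527)/0.0521 = 0.90, so power is 81.5% (the plan states 82%). 176/0.9 = 195.6, hence 196 per group and 392 in total. With all 196 per arm fully ascertained, power is 85%.

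**2. Assumptions for the illustration.** The documents give no share with unknown HF status. Assumed: true rates 50% vs 35%, constant hazard, a share *a* of the arm departing uniformly over 26 weeks, no HF information after departure, 196 per arm.

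With L = −ln(1 − p), the chance that a leaver's event falls before departure is q = 1 − (1 − e^−L)/L.
- Placebo: L = 0.6931, q = 1 − 0.50/0.6931 = 0.2787.
- Drug: L = 0.4308, q = 1 − 0.35/0.4308 = 0.1875.

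**3. Leavers coded event-free after departure.** Observed rate = (1 − a)p + aq.

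| Loss, placebo / drug | Placebo | Drug | Difference | Relative risk | Power |
|---|---|---|---|---|---|
| 0 / 0 | 50.0% | 35.0% | 15.0 points | 0.70 | 85% |
| 10% / 10% | 0.90×0.50 + 0.10×0.2787 = 47.8% | 0.90×0.35 + 0.10×0.1875 = 33.4% | 14.4 | 0.70 | 83% |
| 15% / 5% | 46.7% | 34.2% | 12.5 | 0.73 | 71% |
| 5% / 15% | 48.9% | 32.6% | 16.3 | 0.67 | 91% |

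**4. Leavers dropped unless they already had an event.** Observed rate = [(1 − a)p + aq] / [1 − a(1 − q)].
- 10% / 10%: 0.4779/0.9279 = 51.5% vs 0.3338/0.9188 = 36.3%; difference 15.2 points.
- 15% / 5%: 0.4668/0.8918 = 52.3% vs 0.3419/0.9594 = 35.6%; difference 16.7 points.
- 5% / 15%: 0.4889/0.9639 = 50.7% vs 0.3256/0.8781 = 37.1%; difference 13.6 points.

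With 15% / 5% loss, the same patients give 12.5 or 16.7 points depending only on the coding.

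**5. No true effect.** With a 50% rate in both arms and 15% loss in one arm against 5% in the other, event-free coding gives 46.7% vs 48.9% and a two-sided rejection rate of about 7% instead of 5%. If every event of the leavers is missed, including those before departure, it is about 17%. That is the extreme case.

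**The case against.** The strongest reply has four parts.

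- **Few patients may be affected.** Continued in-person visits are the preferred option after stopping drug, modified follow-up seeks endpoints, and medical information is sought for patients initially lost. Electronic records are abstracted, although for cost outcomes. This stands: the exposed group is mainly full withdrawals and patients traced only through public sources. None of these measures is an analysis rule, and none gives HF status for full withdrawals.
- **The plan may intend to drop leavers.** A reader might infer that patients with unknown HF status fall into the event-free cell. The documents do not say so, and the attrition inflation points towards exclusion. If every leaver is removed, including those with a recorded event, power stays near 81.5% even at 15% / 5%. That result discards observed events and is unbiased only if departure is unrelated to risk. Removing only those with unknown status is biased, as the fourth step of the working shows.
- **The imbalance is hypothetical.** This stands. At 12% placebo and 8% drug, power under event-free coding is about 79%; at 8% and 12% it is about 87%. Equal loss leaves power above the 82% design value.
- **Late deaths.** Because records are searched at the end of the study, a reader might infer that deaths after week 26 would count for leavers only. The sample size section confines the endpoint to the 26-week period, and the search date says when records are checked, not which deaths qualify. A date rule is a clarification.

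Two further readings go too far. Loss does not rest on vital status alone, since missed visits are also required. And no component split supports saying that the composite will consist mostly of HF events, plausible as that is.

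**Conclusion.** The concern holds in this form: loss to follow-up is defined without HF-event status, and the primary method cannot use partial follow-up, so patients known alive with unknown HF status must be counted event-free or dropped, with bias either way. With equal loss of 10% the harm is slight (14.4 instead of 15.0 points, 83% power). With a 15% / 5% split in either direction, the difference runs from 12.5 to 16.3 points under event-free coding and from 13.6 to 16.7 points if leavers without an event are dropped. These figures rest on assumed loss rates, a constant hazard, uniform departure and no HF information after leaving; the mitigations in the protocol would make the true effect smaller. The point merits a change because the coding choice can move the result and should not be made after the data are seen.

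**What to change.** 1. **Lost to follow up patients.** Keep vital-status tracing, and define primary-endpoint completeness separately: HF-event status and vital status both known through day 182 (26 × 7). Record the last date on which HF events were ascertained.
2. **Analysis of Primary Endpoint.** Keep the chi-square and state how incomplete patients enter it. Add, for all randomised patients, a time-to-first-event analysis within 26 weeks: Kaplan-Meier 26-week proportions and a log-rank or Cox test stratified by diabetes status, the randomisation stratum. Censor at the last HF-ascertained contact or day 182, whichever is earlier.
3. **Deaths found only in public records.** Set one rule: none after day 182 counts, and a death after the patient's HF-censoring date enters a sensitivity analysis, not the main censored analysis. Counting such deaths in the main analysis would turn leavers who die into events while surviving leavers are censored early, which biases the rate upward.
4. **Sensitivity analysis.** Impute HF events for patients with vital status only, because censoring assumes non-informative dropout and does not by itself cure unequal loss.

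Cost: protocol and SAP wording, one extra date field and a little more analysis. Adverse event start, hospitalization and death dates are already listed under Variables; the last HF-ascertainment date is not. Reported incomplete follow-up will look higher than under the present definition.

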### **Statistical Methods**

This study is randomized placebo-controlled trial. The overall hypothesis is that dapagliflozin will reduce the rates of the combined outcomes of hospital readmissions, ER visits, clinic visits for HF and death (primary endpoint) and improve symptoms, quality of life and results in a reduction in NT proBNP and resource utilization/costs as compared with placebo in patients with ADHF.

**Sample Size and Power Calculations:** The sample size calculation is based on the primary endpoint measured as the proportion of patients who have hospital readmission, emergency department (ER) visits, and urgent unplanned clinic visit for HF and death during the 26-weeks follow-up period.

Approximately 5.7 million people have been diagnosed with HF in the US . Patients hospitalized for HF are at high risk for readmission, with a 1 and 3-month readmission rate between 20-30%  and a 6-month readmission rate as high as 50% to 60% . An analysis of Medicare data from the Centers for Medicare and Medicaid Services among 28,919 patients with HF hospitalizations, the 6—9 month following the initial HF admission, 60% of patients had 1 or more readmissions for any cause .

Similarly, the national registry of heart failure in Spain with 45.3% of patients with diabetes, a known diagnosis of diabetes was associated with increased all-cause mortality (HR 1.54; 95%CI 1.20–1.97, p = 0.001) and readmissions (HR 1.46; 95%CI 1.18–1.80, p < 0.001). In that study, 40.9% of patients with

diabetes were readmitted within 6-12 months after discharge. An additional study of 462 hospitalized patients with T2D, 44% of the HF events were readmitted to the hospital within 6-month of the primary admission. Thus, our review of the literature indicates that about ~ 40-60% of patients with diabetes with heart failure will be readmitted within 6-month of follow-up.

SGLT2-is have been shown to markedly reduced HF hospital admissions in patients with and without diabetes. In the CVD-Real Study, which included 961 HF cases, SGLT2-i reduced the rates of HF hospitalizations hazard ratio, 0.61; 95% confidence interval, 0.51-0.73; P<0.001. The CVD-Real 2 multinational study of 235,064 patients with T2D, initiation of an SGLT-2i was also associated with a lower risk of all-cause death and hospitalization for heart failure, as compared to other glucose lowering drugs. The use of SGLT-2i vs. other glucose lowering drugs was associated with lower risk of death and heart failure. Recent RCT examining cardiovascular outcome using SGLT2-i reported a significant reduction in hospitalization for HF. In the DECLARE trial, dapagliflozin resulted in lower rate of hospitalization for heart failure compared to placebo (HR, 0.73; 95% CI, 0.61 to 0.88). The EMPA-REG OUTCOME study showed a 35% reduction in HF hospitalizations. In addition, in the CANVAS Program the benefits were greater in patients with a previous history of HF compared with those without HF at baseline (HR, 0.87; 95% CI, 0.72–1.06; P interaction = 0.021). In the Canvas Program, the rate of HF was reduced in patients with history of HF from 28.1% to 14.1% between patients treated with canagliflozin and placebo.

Based on data summarized above, we assume the composite event rate in the placebo group is between 40-60%, which would be reduced by 30% in the dapagliflozin group. Based on two-sided Chi-square test, with preserved alpha=0.05, with 176 subjects, we would achieve over 80% power to detect a 30% reduction in proportion of patients with readmission, ER visits, urgent unplanned clinic visit for HF or death if the composite event rate in the placebo group is 50%. Accounting for 10% attrition, we propose to recruit 392 patients (196 per group).

In the table below, we provide estimated power based on the same method, corresponding to different placebo composite event rates that are between 40-60%:

Composite event rate in the placebo group	40%	45%	50%	55%	60%
Estimated Power	62%	72%	82%	88%	93%

The results in the above table suggest promising power for the proposed study.

We will implement an adaptive design with conditional power calculation and potential for re-estimation of the sample size, if necessary, after the interim analysis scheduled to be performed after 50% of the patients were enrolled and completed the 26 weeks of study period (196 patients) and undergone adjudication of the primary composite endpoint. Sample size re-estimation will be performed based on the observed composite event rate per group at the time of the interim analysis. See below “interim efficacy analysis”.

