## DATA AND SAFETY MONITORING BOARD

An independent Data and Safety Monitoring Board (DSMB) is established and responsible for monitoring the trial according to the protocol to ensure the safety of patients in the trial. During the course of the study, the DSMB will review the cumulative data collected, evaluate the risk/benefit profile. The DSMB plans to meet after every 6 months or after 150 patients are enrolled.

The DSMB would recommend one of the following actions:

1. Continue the study without modification
2. Modify protocol - based on the safety findings may include frequency of safety monitoring, alterations in study procedures. A recommendation on sample size increase/decrease will be considered after the 50% interim efficacy analysis review.
3. Stop the study - because there is overwhelming efficacy or safety concern, i.e., the risks to patients exceed the benefits to be obtained.

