## Interim Efficacy Analysis

For this study, one interim efficacy analysis is planned for the purpose of sample size re-estimation after 50% of the enrolled patients (n=196) have completed the 26 weeks of study period and undergone adjudication of the primary composite endpoint. The process of performing this interim efficacy analysis would, by definition, lead to unblinding of patient treatment to the DSMB. The efficacy analysis and sample size re-estimation will be performed by DSMB members and [name] from the School of Public Health.

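### The unblinded 50% look may change N from per-group event rates, but the primary test stays an ordinary chi-square or Fisher test, so a 5% two-sided error rate is not secured

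*Combined protocol and SAP*

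**What the plan says.** All references are to the combined protocol and SAP.

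- **Statistical Methods, sample size paragraphs.** The base power calculation is "Based on two-sided Chi-square test, with preserved alpha=0.05", for a 50% placebo event rate "which would be reduced by 30% in the dapagliflozin group". It gives 196 per group, 392 in all, after 10% attrition.
- **Statistical Methods, adaptive-design paragraph.** The design is adaptive "with conditional power calculation and potential for re-estimation of the sample size, if necessary". On the basis for the change: "Sample size re-estimation will be performed based on the observed composite event rate per group at the time of the interim analysis".
- **Interim Efficacy Analysis.** At half the patients (n=196), "one interim efficacy analysis is planned for the purpose of sample size re-estimation". On blinding: "The process of performing this interim efficacy analysis would, by definition, lead to unblinding of patient treatment to the DSMB".
- **Data and Safety Monitoring Board.** "A recommendation on sample size increase/decrease will be considered after the 50% interim efficacy analysis review".
- **Analysis of Primary Endpoint.** The proportions with an event are compared "between the two study groups, using Chi-squares test", with Fisher's exact test as the alternative.
- **Stopping Due to Overwhelming Evidence of Efficacy.** Group sequential testing takes place when 70% of randomized patients have been followed and adjudicated, using the gamma family with parameter -5.

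The document gives no re-estimation rule, conditional-power zone, cap or floor on N, combination or weighted statistic, or final nominal level.

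**The concern.** Two arm-specific event rates together give the interim treatment effect. If the remaining sample size depends on them, the ordinary final statistic no longer has its nominal null distribution. With first-half statistic z1 at information 0.5 (planned total = 1) and final information n, the ordinary statistic is

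Z = √(0.5/n)·z1 + √(1 − 0.5/n)·z2,

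where z2 comes from the later patients. If n depends on z1, so does the weight on z1. Raising n after a weak first half dilutes it, and lowering n after a strong first half protects it. Both can push the rejection rate above 5%.

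Gamma spending does not repair this. It accounts for testing twice on a schedule that is independent of the observed effect. The validity of the primary p-value is at stake, and a statistic or rule chosen after arm-level rates have been seen cannot be defended as pre-specified.

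**Working it through.** **1. The plan's own figure.** Placebo 0.50, dapagliflozin 0.7 × 0.50 = 0.35, n = 176 per group, pooled rate 0.425.

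- Null SE = √(2 × 0.425 × 0.575/176) = 0.0527. Alternative SE = √((0.25 + 0.2275)/176) = 0.0521.
- Power = Φ[(0.15 − 1.96 × 0.0527)/0.0521] = 81.5%; the table states 82%.
- 176/0.9 = 195.6, so 196 per group and 392 in total, as stated.

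**2. What gamma(-5) implies.** Cumulative spend at fraction t is 0.05(e^{5t} − 1)/(e^5 − 1). At t = 0.7 this is 0.05 × 32.1/147.4 = 0.0109, so |Z| = 2.546. The remaining alpha gives 1.9835 at the end, nominal p = 0.0473. Leaving 1.96 at the end gives 5.26% even with N fixed.

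**3. Adding the re-estimation.** The plan gives no rule, so the following is assumed. Conditional power under the observed trend is

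CP(n) = Φ[(z1·n/√0.5 − 1.9835√n)/√(n − 0.5)].

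N is moved within the allowed range towards CP = 80%. The efficacy test falls at 70% of the revised N, and the boundaries are those in step 2. Null simulation, 4,000,000 trials per rule (Monte Carlo SE 0.011 points):

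| Assumed rule | N reacts to favourable trend only | N reacts to either direction |
|---|---|---|
| N fixed | 5.00% | 5.00% |
| Increase only if CP ≥ 0.41, cap 1.5× | 4.96% | 4.93% |
| Any increase, cap 1.5× | 5.36% | 5.72% |
| 0.75× to 1.5× | 5.70% | 6.40% |
| Pre-fixed stage weights, every rule above | 4.99% | 4.99% |

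**4. Patient-level check.** Binary outcomes, ordinary chi-square, 88 then 176 evaluable per arm, 2,000,000 trials per cell, null rates 35% / 42.5% / 50%:

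- N fixed: 5.08 / 4.92 / 5.20%.
- Any increase to 1.5×: favourable 5.41 / 5.30 / 5.59%; either direction 5.75 / 5.67 / 5.98%.
- 0.75× to 1.5×: favourable 5.73 / 5.67 / 5.86%; either direction 6.41 / 6.38 / 6.50%.
- CP ≥ 0.41 zone, favourable: 5.03 / 4.91 / 5.19%.
- Blinded pooled-rate re-estimation: 5.02 / 5.01 / 5.18%.

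**5. Two readings that shrink the excess.** Both were simulated at the same three null rates.

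- Fisher's exact test: 3.7-4.0% with N fixed; 4.2-4.4% (favourable) and 4.5-4.8% (either) for any increase to 1.5×; 4.4-4.6% and 5.1-5.2% for 0.75× to 1.5×.
- Chi-square, updating only the placebo rate with the 30% reduction held fixed: 4.9-5.2%, at most about 0.25 points above fixed N.

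**6. The levels depend on where the 70% test falls.**

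- If it stays at 70% of the original N (0.7 × 392 = 274) and N rises 1.5 times to 588, its information fraction is 0.7/1.5 = 0.47. Using 0.0109 and 0.0473 with ordinary statistics then gives 5.29%.
- If 274 completers are set against 352 evaluable, the fraction is 0.778 and the gamma(-5) levels are 0.0163 and 0.0464.

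**The case against.** The strongest reply is that the plan has not been shown to exceed 5%. It mentions conditional power, and an increase-only zone would hold the level with the ordinary test. Fisher's conservatism absorbs the excess under every benefit-driven rule tried. Per-group rates could also mean updating the placebo rate alone, as the plan's power table does. The highest figures need N to react to harm as well as benefit, and need a decrease, which the board would only consider.

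Room for a decrease depends on accrual, which the documents do not give. With even accrual over m months, about 196 + 6 × 392/m patients are enrolled at the look: 392 for m = 12 (no decrease possible), 327 for m = 18, 294 for m = 24.

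Most of this stands, and it limits the size of the point. It does not remove it. No zone is stated, a decrease is expressly open, the choice between chi-square and Fisher is left open, and the mention of conditional power fits a comparative re-estimation at least as well as a placebo-rate update.

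Three stronger readings should be resisted.

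- A reader might infer that the plan asserts an alpha preserved through the adaptation. The phrase is the input to the base power calculation and comes before the adaptive design is introduced.
- A reader might infer that the 50% look is an unprotected chance to stop for efficacy. Its stated purpose is re-estimation, and efficacy stopping has its own section at 70%. One confirming sentence is enough.
- A reader might infer that the power claim fails at the adjusted final level. It becomes 80.9%, so the statement of more than 80% remains true.

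**Conclusion.** The concern holds in this form: the primary test's two-sided 5% level is not secured, because N may be raised or lowered from unblinded arm-level data while the final statistic is an ordinary one and the rule is unstated. That the level is actually exceeded does not follow from the documents.

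The excess is modest and depends on the rule. With chi-square and an 80% conditional-power target it is about 0.4-0.7 points for any increase to 1.5 times and 0.7-1.4 points when N may also fall to 0.75 times. It is nil with a zone starting at 0.41, and little or nothing with Fisher or a placebo-rate-only update. These are illustrations under assumed rules and do not bound the error. The matter should be settled before the 50% look, because it cannot be settled credibly afterwards.

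**What to change.** Before the 50% look, adopt one of the following in the SAP and the board's charter.

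- **(a) Preferred.** Keep arm-level re-estimation and make the primary test a Cui-Hung-Wang statistic with pre-fixed stage weights. For example, use information fractions 0.5/0.2/0.3, so that stage z-statistics are weighted by their square roots 0.707, 0.447 and 0.548, with gamma(-5) levels 0.0109 and 0.0473 matched to those weights. This holds 5% whatever rule sets N. If the efficacy test is at 70% of the revised N, that N must exceed 196/0.7 = 280 for the test to follow the 50% look.
- **(b)** Re-estimate from the blinded pooled event rate with the 30% reduction held fixed, increase-only, with a stated cap.
- **(c)** Keep the ordinary test, drop the decrease option, and allow increases only in a pre-specified conditional-power zone shown to hold 5%. A lower limit of 0.41 with a 1.5× cap suffices; 0.20 also gave 5.0% in simulation.

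Under (b) and (c), compute the gamma(-5) levels from the actual information fraction of the 70% test relative to the final, possibly revised, N; do not fix them at 0.0109 and 0.0473. In all cases state whether 70% refers to the original or the revised N, name either chi-square or Fisher as the single primary test, and confirm that efficacy stopping belongs to the 70% test only.

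**Cost.** Wording, plus about 0.6 points of power: at 1.9835, Φ[(0.15 − 1.9835 × 0.0527)/0.0521] = 80.9% against 81.5%. Option (b) with a 1.5× cap would raise power at a 40% placebo rate from 66% by the formula in step 1 (the plan's table says 62%) to 79%, at a mean of 241 evaluable per arm.
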